#### **4.5 POST PROCEDURE FOLLOW-UP EVALUATIONS**

All trial subjects will be followed through hospital discharge and will undergo follow-up evaluations for a total of 36 months at the following time points:

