#### 5.3.6.5 OTHER SAFETY DATA

Concomitant medications and AEs will be summarized at each follow-up visit. In addition, tables and listings will be provided.

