4. STUDY OBJECTIVES

The primary objective of this study is to assess the safety and efficacy of the iCAST™ RX Stent System in subjects with resistant hypertension associated with de novo atherosclerotic renal artery disease. The primary objective will be evaluated using co-primary endpoints. The primary functional endpoint will assess safety and effectiveness based on the primary patency rate at 9-months on a per lesion basis evaluated against a performance goal of published studies with bare-metal stents. The primary clinical endpoint will assess the improvement in Systolic Blood Pressure (SBP) at 9-months as compared to baseline SBP.

The secondary objectives of this study are:

- 1) To evaluate the occurrence of procedure-related Major Adverse Events (MAEs) reported as percentage of subjects with MAE, at 30-days, 9-months, 12-months, 24-months, and 36-months.
Inclusive of:
 - i) Procedure-or device-related occurrence of death
 - ii) Q-Wave myocardial infarction (MI)
 - iii) Clinically driven target lesion revascularization (TLR)

Amendment #1: 15Jul13

Confidential

- (1) Defined as a TLR (Percutaneous Balloon Angioplasty (PTA), bare metal stent or repeat covered stent deployment, or surgical bypass) due to documented recurrent hypertension from 30-days post-procedure level and/or deterioration in renal function from baseline value, associated with angiographic core laboratory adjudication of a \geq 60% diameter covered stent restenosis.
- iv) Significant embolic events
 - (1) Defined as unanticipated kidney/bowel infarct clinically driven by symptoms of abdominal or back pain and confirmed with Computed Tomography (CT) scan or open surgery, lower extremity ulceration or gangrene, or kidney failure after 30-days, 9-months, 12-months, 24-months, and 36-months.

MAEs were reviewed and adjudicated by the Clinical Event Committee. The adjudicated data will be used to perform the analysis of this endpoint.

- 2) To determine technical success defined as successful delivery and deployment of the iCAST™ RX Stent System with \leq 30% residual angiographic stenosis after covered stent deployment (including post-dilatation) assessed via Qualitative Vascular Analysis (QVA) by an independent core laboratory.
- 3) To determine acute procedural success defined as technical success without the occurrence of MAE prior to hospital discharge.

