7.1 Schedule of Evaluation

Table 2 SCHEDULE OF EVENTS

	(-14)-Days (Medical Documentation Screening period) ⁷ Prior to Procedure	(-7)-Days ⁷ Prior to Procedure	Day 0 Procedure	30-Days (+14/-7 Days) Office Visit	6-Months (+/-30 Days) Phone Call	9-Months (+/-30 Days) Office Visit	12-Months (+/- 30 Days) Office Visit	18-Months (+/-30 Days) Phone Call	24-Months (+/- 60 Days) Office Visit	36-Months (+/- 60 Days) Office Visit
Informed Consent	X									
General Entry Criteria	X									
Angiographic Entry Criteria			X							
Demographics and Medical History	X									
Weight (Kg)/ Height (cm)	X									
Vital Signs	X		X	X		X	X		X	X
BP Assessment¹	X ¹	X ¹	X	X		X	X		X	X
Laboratory Assessments²	X ²		X ²	X ²		X ²				
Test for Proteinuria³	X ³									
Physical Exam	X		X	X		X	X		X	X
Pregnancy Test⁴	X ⁴		X ⁴							
iCAST™ RX			X							

Confidential

	(-14)-Days (Medical Documentation Screening period) ⁷ Prior to Procedure	(-7)-Days ⁷ Prior to Procedure	Day 0 Procedure	30-Days (+14/-7 Days) Office Visit	6-Months (+/-30 Days) Phone Call	9-Months (+/-30 Days) Office Visit	12-Months (+/- 30 Days) Office Visit	18-Months (+/-30 Days) Phone Call	24-Months (+/- 60 Days) Office Visit	36-Months (+/- 60 Days) Office Visit
Stent System Placement										
Duplex Ultrasound				X		X				
Angiography⁵			X ⁵			X ⁵				
Concomitant Medications	X	X	X	X	X	X	X	X	X	X
Adverse Events⁶	X	X	X	X	X	X	X	X	X	X

¹A minimum of two office visits are required within the 14-day Medical Documentation Screening period. If the procedure is scheduled > 14 days from the first office visit, subjects should return every two weeks (+/- 3 days) for BP assessments and monitoring.

²Chem12 panel which includes: Glucose, Calcium, Albumin, Total protein, Sodium, Potassium, CO2, Chloride, BUN, creatinine, ALP, ALT, AST, and bilirubin.

³Test for proteinuria should be completed for subjects during Step 2 of the Medical Documentation Screening Period.

⁴Pregnancy test required at screening and on the day of procedure for females of childbearing potential only.

⁵ All subjects must have angiography to determine percent diameter stenosis prior to treatment and at 9-months (if DUS indicates $\geq 60\%$ stenosis).

⁶AE collection (serious and non-serious) will begin upon completion of the ICF process through the 9-month follow-up visit, thereafter only SAEs and UADEs will be recorded.

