Medications will be tabulated using frequencies and percentages. Subjects may have more than 1 medication per ATC text. At each level of subject summarization, a subject will be counted once if he/she reports one or more medications. Percentages will be based on the number of subjects in the ITT analysis population.

In addition, the number and percentage of subjects using antihypertensive concomitant medications will be summarized by pre-defined categories as recorded in the electronic case report form (eCRF) (diuretics, beta blockers/calcium channel blocker and ACE/ARBs) and presented overall and by study visit.

Use of anti-platelets medication from hospital discharge to three months will be described as the percentage of subjects taking anti-platelet medication at the 3-month follow-up visit.

A subject listing will be presented and include at minimum the medication, drug classification, start and stop dates.

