9.11.4. Anticipated Adverse Events

Based on the literature and on clinical and commercial experience with implantation of a covered stent in human arteries,

Table 4: Anticipated AEs, includes anticipated AEs that have been identified as possible complications:

Table 4: Anticipated AEs

 ○ Abdominal Pain ○ Abscess ○ Acute or sub-acute thrombosis ○ Acute myocardial infarction ○ Allergic reaction to stainless steel, drugs, contrast agent, or anti-platelet agents ○ Aneurysm ○ Arrhythmias, including Ventricular Fibrillation (VF) and Ventricular Tachycardia (VT) ○ Arteriovenous (AV) fistula ○ Bowel infarct ○ Death ○ Dialysis ○ Emboli (air, tissue, or thrombotic) resulting in tissue ischemia or infarction ○ Emergency surgery to correct vascular complications ○ Extremity ischemia/amputation ○ Fever ○ Hemorrhage ○ Hematoma 	
 ○ Hypotension or hypertension ○ Inadequate implantation or Intimal trauma ○ Inadvertent exclusion of branch or accessory vessel ○ Incision site pain or infection ○ Injury, dissection, perforation, or rupture of the vessel ○ Kidney infarct ○ Myocardial infarction or ischemia ○ Nephrectomy ○ Pseudo-aneurysm formation ○ Pyrogenic reaction ○ Renal insufficiency or failure ○ Restenosis of stented lesion ○ Sepsis/infection ○ Stent embolization ○ Stent migration/stent misplacement ○ Stroke or other cerebrovascular accident ○ Thromboembolic event ○ Tissue necrosis or ulceration ○ Total occlusion ○ Vessel spasm
---	--

The study main safety outcome is the incidence of subjects with any adverse event

Amendment #1: 15Jul13

Confidential

observed after the study procedure over the totality of the study. An overall summary that includes the incidence of subjects with any adverse event during the entire study, the number of AEs and the number and percentage of subjects who experienced at least one AE will be presented. This summary will also include all AEs, serious AEs (SAEs), unanticipated adverse device effects (UADE), procedure-related AEs, procedure related SAEs and AEs with outcome of death.

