Adverse event data summaries will be presented by System Organ Class (SOC) and Preferred Term (PT). AEs will be summarized using discrete summary statistics at the subject and event level by SOC and PT. If a subject reports the same PT multiple times within the same SOC, that PT will only be reported once within that SOC. As with the PT, if a subject reports multiple conditions within the same SOC, that SOC will only be reported once.

To count the number of subjects with any AEs, if a subject has multiple AEs coded to the same PT within the same SOC, the subject will be summarized within the maximal severity. For the summary of maximal severity, if the subject has multiple AEs of the same PT and of different grades of severity, the maximal severity will be reported. In the summary, SOC will be listed in ascending alphabetical order; PTs will be listed in order of descending frequency for all subjects within each SOC.

Separate summaries of the AEs stratified by before or after study procedure will be provided for the following categories:

- Adverse Events (AE)
- Procedure-Related AEs
- Unanticipated Adverse Device Effects (UADEs)
- Serious AEs (SAE)
- Serious Procedure Related AEs (separate for CEC adjudicated events and Investigator)
- Fatal AEs

All AEs will be presented in a subject listing. In addition, UADEs will be provided in a
Amendment #1: 15Jul13

separate listing.

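### The SAP drops the protocol's by-visit adverse event summaries without declaring it, so its general AE and SAE tables pool all time after the procedure

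*SAP*

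**What the plan says.** Protocol 5.3.6.5 states: "Concomitant medications and AEs will be summarized at each follow-up visit". Under Protocol 4.5, subjects "will undergo follow-up evaluations for a total of 36 months".

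SAP 9.11.4 plans an overall summary that includes "the incidence of subjects with any adverse event during the entire study", and defines the main safety outcome as the incidence of subjects with any AE "observed after the study procedure over the totality of the study". Tables by system organ class, preferred term and maximal severity follow. The time split is given in one sentence: "Separate summaries of the AEs stratified by before or after study procedure will be provided for the following categories". The categories are AEs, procedure-related AEs, UADEs, SAEs, serious procedure-related AEs (shown separately for committee-adjudicated and investigator-reported events) and fatal AEs. All AEs are also listed by subject.

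The footnote on AE collection in the SAP 7.1 schedule says that all AEs are collected through the 9-month visit and "thereafter only SAEs and UADEs will be recorded".

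Two other parts of the SAP keep time points. Antihypertensive drug use in SAP 9.8 is "presented overall and by study visit". The MAE objective in SAP section 4 is "reported as percentage of subjects with MAE, at 30-days, 9-months, 12-months, 24-months, and 36-months".

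**The concern.** One protocol sentence covers both concomitant medications and AEs. The SAP keeps by-visit output for antihypertensive drugs and omits it for AEs, without saying so.

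This is a single-arm, open-label trial (SAP 5.3 and 5.4). With no comparator, the time of an event relative to stent placement is one of the few objective ways to separate the harm of the procedure from the background illness of these patients. Attribution by an investigator or committee helps, but it is a judgement. A table with one stratum after the procedure does not show whether serious events cluster in the first month or accrue evenly over follow-up.

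**Working it through.** No sample size, power or error rate is involved. The check is a comparison of the texts, followed by a small illustration.

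**1. Commitment against plan.** Appendix 4 of the protocol schedules AE collection at seven contacts after the procedure: 30 days and 6, 9, 12, 18, 24 and 36 months. The tables in SAP 9.11.4 have one stratum after the procedure covering all seven.

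**2. Is the change declared?** SAP section 2 covers the exploratory status of inference and the absence of imputation. SAP 6.2 repeats these and lists three changes: no imputation, sensitivity analysis limited to the per-protocol population, and a time-to-event analysis of revascularization. AE tabulation is in neither.

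**3. How long is the pooled period?** It differs by type of event. Non-serious AEs are recorded only to the 9-month visit; SAEs and UADEs to 36 months. The main safety outcome combines both recording regimes in one proportion.

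**4. What does the SAP separate in time or by cause elsewhere?**

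| Output | SAP section | What it separates |
|---|---|---|
| MAEs | 4, 7.2 | 30 days; 9, 12, 24, 36 months (the derivation in 7.6.2 is one indicator with no time point) |
| Acute procedural success | 7.6.2 | MAEs before discharge |
| Procedure-related AEs and SAEs | 9.11.4 | Attribution, not timing |
| All-cause death | 9.11.13 | Kaplan-Meier to 9 months |
| eGFR, laboratory values | 7.6.2, 9.11.6 | 30 days, 9 months |
| Angiographic complications, including dissection and perforation | 9.11.10 | Baseline and procedure; 9 months |

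**5. What is left?** MAEs have four components: procedure- or device-related death, Q-wave MI, clinically driven TLR and significant embolic events. Hemorrhage, hematoma and emergency vascular surgery are on the SAP's list of anticipated AEs but are not MAE components and appear in no other row above, except where they are judged procedure-related. The same is true of SAEs taken as a whole.

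**6. Two features that blur the single stratum further.** SAP 9.11.1 counts an AE as occurring after the procedure if it ends on or after the procedure date, is ongoing, or has no end date. AEs are collected from consent, so an event that began during screening can enter that stratum. Also, SAP 7.2 places the endpoint evaluation when the last enrolled subject completes 9 months. Earlier enrollees will by then have been followed longer, so a crude proportion from AE tables run at that cut would mix follow-up lengths.

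**7. Illustration (assumed counts).** SAP 6.1 gives 68 enrolled subjects. Suppose six different subjects each have one serious bleed, and all 68 remain in follow-up.

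| Pattern | Day 0–30 | Day 31 to 9 months | After 9 months | SAP 9.11.4 SAE row |
|---|---|---|---|---|
| All early | 6/68 = 8.8% | 0 | 0 | 6/68 = 8.8% |
| Evenly spread | 2/68 = 2.9% | 2/68 = 2.9% | 2/68 = 2.9% | 6/68 = 8.8% |

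The planned SAE row is the same in both cases; the interval table is not. The procedure-related SAE tables could still differ between the two patterns, depending on attribution.

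**The case against.** The strongest defence is that much of the early-harm picture survives. A reader might infer that harm around the procedure cannot be told from later events at all. The documents do not support that: the table in step 4 shows several outputs that separate them, and every AE is listed by subject in a trial of 68. A reader might also infer that all AEs are pooled over three years. Non-serious AEs are not; their recording stops at the 9-month visit. Nor do renal decline or vessel dissection and perforation belong among the unreported early harms, because eGFR at 30 days and core-laboratory angiography capture them. Protocol Table 6 tempts one to test early bleeding against its anticipated percentages, but it gives no time horizon, so treating them as 30-day benchmarks would be an assumption. All of this stands and narrows the point.

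Other defences carry less weight. SAP section 11 refers to table mocks that are not in these documents and may contain by-visit tables; if so, the SAP text should say so. Procedure-related tables are not a substitute for timing, and Protocol 6.3.2 defines relatedness grades for the device only. The listing is not a summary, and its fields are not specified. Early termination explains the loss of formal inference and imputation, but not a coarser description of safety.

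Finally, three onset intervals are not a summary at each visit either. That is correct, and it is why the replacement has to be declared.

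**Conclusion.** The discrepancy is real and undeclared. As written, the AE, SAE, UADE, procedure-related and fatal AE tables in SAP 9.11.4 pool all time after the procedure: to 9 months for non-serious AEs, to 36 months for SAEs and UADEs. The practical gap is the lack of any planned early-period rate for hemorrhage, hematoma, emergency vascular surgery and SAEs in general.

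The size is moderate. No primary endpoint, decision rule or data collection is affected, and the SAP already treats all inference as descriptive. It still merits correction, because safety is part of the primary objective and there is no control group. The conclusion rests on the SAP text alone and assumes that the unseen table mocks do not already supply these tables. The counts in the illustration are assumed and say nothing about the trial's actual event rates.

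**What to change.** In SAP 9.11.4, keep the split before and after the procedure and add tables of post-procedure AEs, SAEs, procedure-related AEs and SAEs, and fatal AEs by onset interval:

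- day 0 to 30;
- day 31 to the 9-month visit;
- after the 9-month visit, for SAEs and UADEs only.

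Use as denominator the subjects still in follow-up at the start of each interval. Because the intervals go by onset date while SAP 9.11.1 also counts events by end date, show events with onset before day 0 separately, and state how partial onset dates are assigned.

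In SAP 6.2, record that these intervals replace the by-visit AE summaries of Protocol 5.3.6.5. Declaring the change without adding the tables would settle the inconsistency but leave the gap in early rates.

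The cost is one derived variable and some extra table columns, with no new data. Counts per interval will be small, so the tables should be read descriptively.

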9.11.5. Device Failures, Malfunctions and Near Incidents

Investigators are instructed to report all possible device failures, malfunctions or near incidents observed during the course of the trial, to Atrium. In addition, these incidents will be documented in the eCRF provided as follows:

- Device Failure: A device failure has occurred when the device is used in compliance with the IFU, but does not perform as described in the IFU and also negatively impacts treatment of the trial subject.
- Device Malfunction: A device malfunction occurs when an unexpected change to the device that is contradictory to the IFU is observed, which may or may not affect device performance.
- Device Misuse: Any use of the investigational device by an investigator that is contradictory to the application described in the IFU will be categorized as device misuse.

The overall number of reported device malfunctions, failures and misuses will be summarized using descriptive statistics (counts and percent).

In addition, a subject listing of the device information will be provided and include:

- Subject ID/lesion
- Lot number/Reference number
- Length/Diameter/Catheter length
- Device performance issue related to the procedure
- Type of device incident
- Type of device failure
- Problem with balloon/Type
- Adverse event associated with device performance issue

9.11.6. Clinical Laboratory Evaluations

Confidential

A chemistry 12 panel which includes: Glucose, Calcium, Albumin, Total protein, Sodium, Potassium, CO₂, Chloride, BUN, creatinine, ALP, ALT, AST, and bilirubin will be collected at baseline, 30-days and 9-months of study follow-up.

The change from baseline will be defined as the follow-up visit value minus the baseline visit value. Laboratory values will also be classified as normal (if value is within normal reference range) or abnormal (if value is either below or above the normal reference range). The clinical significance of the laboratory results will be determined by the clinical investigator.

Clinical laboratory results will be converted into standard units and summarized descriptively (number of observations, standard deviation, median, min and max) using observed values and the change from baseline values.

A subject listing of the clinical laboratory parameters will be also provided and include at minimum subject ID, date/time of assessment, laboratory test, results/units, clinical significance and investigator's comments.

9.11.7. Vital Signs

Vital signs, including pulse, respiratory rate, oral temperature and systolic (SBP)/diastolic blood pressure (DBP) (mmHg) will be summarized with continuous descriptive statistics (number of observations, standard deviation, median, min and max) at baseline, follow-up visits and change from baseline (only for the SBP/DBP), where change from baseline is defined as the follow-up visit value minus the baseline visit value.

Additionally, a subject listing of the vital signs results will also be produced including at minimum date of assessment, study visit and results.

Both systolic and diastolic blood pressures will be measured in triplicate at each time point and the average of the non-missing measurements will be used.

9.11.8. Duplex Ultrasound (DUS)

Amendment #1: 15Jul13

Confidential

Follow-up DUS of the target renal artery will be performed at 30 days and 9-months of study follow-up. The count and percentage of subjects in the ITT population with a DUS indicative of <60% or ≥ 60% stenosis will be presented at each study follow-up visit.

A subject listing with the DUS results will be presented and include at a minimum: subject ID, visit, result, date of duplex ultrasound.

9.11.9. Physical Examination

Physical Examination was determined by the investigator as normal or abnormal at each assessment. Changes from baseline will be analyzed as no change from baseline (including normal to normal and abnormal to abnormal), abnormal to normal and normal to abnormal. Changes from baseline that were determined by the investigator to be clinically significant were recorded as adverse events.

Physical exam findings will be presented in a subject listing and include at minimum date of assessment, study visit, exam (body system), findings and investigator's comments.

9.11.10. Angiographic Results and Revascularization

Angiographic Results

The degree of stenosis, baseline angiographic core lab results, procedural characteristics and post-procedure angiographies core lab results will be summarized using descriptive statistics at baseline and at the 9-months of study follow-up.

A subject listing of the angiographic results will include:

- Subject ID/Lesion
- Target artery
- Type of treatment
- Revascularization/Type of treatment required
- Guiding catheter
- Evidence of stenosis within original treatment are

Amendment #1: 15Jul13

Confidential

- Target lesion length (mm)
- Pole to pole kidney length (mm)
- Ostial lesion
- Length of stenosis from ostium (mm)
- Minimal lumen diameter (MLD) (mm)
- Reference vessel diameter (RVD) (mm)
- Length of stent outside renal aorta (mm)
- Reference area (mm²)
- Calcification/Location
- Aneurysm/Size (cm)
- Thrombus
- Eccentric lesion
- Ulcerate plaque
- Abrupt closure
- Spasm
- Distal embolization
- Perforation
- Thrombus in Myocardian Infarction (TIMI) flow pre/post
- Dissection/Grade
- Number of accessory renal arteries
- Per Accessory Renal Artery
 - % Stenosis
 - MLD (mm)
 - RVD (mm)

9.11.11. Revascularization

The total number of subjects with additional treatments to the target vessel will be summarized by counts and percents. In addition, the cumulative probability of target vessel revascularization by 9-months will be computed using the life-table method.

The following SAS code will be used:

Amendment #1: 15Jul13

```
PROC LIFETEST DATA = ADTT;  
  TIME DURATION * CENSOR (0);  
  STRATA TREAT;  
  RUN;
```

Time to revascularization is defined as the time from date of procedure until date of revascularization. For each lesion that has not undergone revascularization, it will be censored at the time of last contact date known to be alive (contacts considered in the determination of last contact date include adverse event date, vital signs, and last known alive date from Study Exit page of eCRF).

Where:

Time to Revascularization = (Date of Revascularization – Date of Procedure +1)

In order to provide visualization of the estimated probability of an event, a cumulative incidence plot of the target vessel revascularization will be presented.

A subject listing with the revascularization information will be also presented and include:

- Subject ID/Lesion
- Date of procedure
- Number of target/non-target lesions treated
- Indication for revascularization
- Lesion Location
- Lesion Type
- Pre-procedure % diameter stenosis
- % stenosis

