6.2 Changes from the Analyses Planned in the Protocol/CIP

Due to the early termination of enrollment for Protocol/CIP No. iCAST™ RX-ARAS-001, all inferential analysis should be interpreted as descriptive and will be carried out in an exploratory manner.

The following changes were applied:

1. Missing data will not be imputed.
2. Sensitivity analysis will be limited to evaluating the primary analysis results using the per protocol population.
3. Supportive analysis of the revascularization information using a time to event approach will be performed.

Confidential

7. BASELINE, EFFICACY and SAFETY EVALUATIONS

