7.4 Visit Windows

The time schedule described in the protocol for each scheduled activity will be followed as closely as possible. The protocol allowable visit windows in Table 3.1 below will be utilized for analysis purposes. All scheduled visits will be windowed according to the table below.

Table 3.1: Primary Visit Windows

Protocol Visit	Target Day	Protocol allowable window (days)
Screening I (Day -14)	-14	-
Screening II (Day -7)	-7	-
Baseline (Day 0)	0	-
Visit 1 (Day 30)	30	+/- 7 (23 – 44)
Visit 2 (6-Months)	182	+/- 30 (152 – 212)
Visit 3 (9-Months)	273	+/- 30 (243 – 303)
Visit 4 (12-Months)	365	+/- 30 (335 – 395)
Visit 5 (18-Months)	575	+/- 30 (545 – 605)
Visit 6 (24-Months)	730	+/- 60 (670 – 790)
Visit 7 (36-Months)	1095	+/- 60 (1035 – 1155)

If a subject has more than one assessment occurring in the same analysis visit window, the data from the visit closest to the scheduled (target) study day will be used for summaries. If two assessments have the same distance from the scheduled study day, the assessment after the scheduled study day will be used.

If two assessments both occur on the protocol-specified day, and both are valid, then the later one will be summarized. All assessments will be provided in the data listings.

The 9-month primary endpoint analysis will be based on the protocol allowable visit windows. Supportive analysis of the primary efficacy endpoint will be performed using a time to event analysis.

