7.6 Endpoints, Safety Outcomes and Other Parameters

7.6.1.Primary Endpoints

Primary Patency Rate

In order to mitigate the challenges with DUS interpretation, clinical validation through independent noninvasive core laboratory and/or angiography will be performed in order to correctly validate and definitively assess percent diameter stenosis. DUS is highly reliable in identifying widely patent stents – however, correlation studies of DUS with angiography have confirmed that DUS is not as accurate when results suggest a stenosis. To lessen the risk of inaccurate readings, if a stenosis is detected in DUS (RAS > 60%) or if the DUS is non-diagnostic due to an imaging quality problem then a contrast angiogram will be used to assess the degree of restenosis of the covered stent(s) at the 9-month visit (± 30 days).

The primary efficacy variable is the primary patency rate, defined as continuous patency without the occurrence of a total occlusion (complete obstruction or a closure of a passageway or vessel determined by DUS or contrast angiogram) of the original lesion, and

Amendment #1: 15Jul13

Confidential

- without a re-intervention due to a clinically driven restenosis or occlusion to treat a partial or total occlusion of the stented segment,
- or bypass of the stented segment due to clinically-driven restenosis or occlusion

The primary patency will be calculated on a per lesion basis – for purpose of analysis in cases in which multiple lesions are covered by one stent then the stented segment will be considered as one lesion. The cumulative incidence of patency at 9 months will be computed as the number of lesions that met primary patency divided by the number of subject-lesions for the population being analyzed.

Change from Baseline in Systolic Blood Pressure

Systolic blood pressure will be assessed at each follow-up study visit. Blood pressure measurements will be obtained with a certified, calibrated, and validated equipment. Subjects will be instructed to refrain from exercise, smoking or caffeine ingestion for 30 minutes before blood pressure measurement, and measurements will be obtained after at least 5 minutes of rest. At each time point, a minimum of three (3) readings separated by 2 minutes will be averaged.

The primary clinical outcome is the improvement in systolic blood pressure (SBP) at 9-months as compared to baseline systolic blood pressure computed as follows:

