9.11.13. Mortality

The number and percent of all cause deaths will be reported throughout the study or at the cutoff date for DSMB. The Kaplan-Meier estimate of the death free-survival curve by 9-months of study follow-up will be presented. Death-free survival is defined as the time (months) from the date of the procedure (stent placement) to the date of death of any cause. For each patient that has not known to have died, these will be censored at the time of last contact date known to be alive (contacts considered in the determination of last contact date include adverse event date, vital signs, and last known alive date from Study Exit page of eCRF).

A detailed listing of deaths will be provided and include: subject ID, date of procedure, date of death, relatedness to the study device, primary cause of death, investigator's comments.

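### The time-to-event support promised for primary patency is specified only as time to target vessel revascularization, which is a different event

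*SAP*

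**What the plan says.** Three sections of the SAP describe the added analysis differently.

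- SAP 7.4 (Visit Windows): "Supportive analysis of the primary efficacy endpoint will be performed using a time to event analysis".
- SAP 6.2 (Changes from the Analyses Planned): "Supportive analysis of the revascularization information using a time to event approach will be performed".
- SAP 9.11.11 (Revascularization): "the cumulative probability of target vessel revascularization by 9-months will be computed using the life-table method". The clock is given by "Time to revascularization is defined as the time from date of procedure until date of revascularization", and the censoring rule begins "For each lesion that has not undergone revascularization, it will be censored at the time of last contact date known to be alive". No exception is made for an occluded lesion.

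The endpoint named in 7.4 is set in SAP 7.6.1: "The primary efficacy variable is the primary patency rate, defined as continuous patency without the occurrence of a total occlusion" of the original lesion. It also requires no clinically driven re-intervention and no clinically driven bypass of the stented segment. Total occlusion may be found by duplex ultrasound (DUS) or contrast angiogram, and it is a failure whether or not it is treated.

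No other section supplies a time-to-event analysis of patency. SAP 9.9.3 limits sensitivity analysis to the per-protocol population, and 9.9.5 plans no exploratory efficacy analyses. SAP 9.10.3 mentions time-to-event summaries for other secondary endpoints but gives no event or censoring rule. The only other curve with a stated event is all-cause death (9.11.13).

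On method, 9.11.11 says life-table. Its SAS code calls PROC LIFETEST with no method option, treats value 0 of CENSOR as censored without defining the coding, and stratifies by TREAT. SAP 8.1 says Kaplan-Meier for time-to-event analyses, and SAP 5.3 says the study has a single arm.

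**The concern.** A supportive analysis is useful when it looks at the same quantity by another route. Here the route changes and so does the quantity. Followed as written, the plan would put beside the patency rate a curve that ignores the gravest patency failure unless someone re-treats it, and that adds procedures the patency definition does not count.

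This matters more because the SAP has removed imputation (2, 6.2, 8.3) and analyses patency on observed data only (9.9.1). A time-to-event analysis is the one planned approach that could use partial follow-up from subjects who leave before the 9-month visit. If it measures another event, that use is lost. Agreement between the two results would not be evidence of robustness, and disagreement could not be interpreted.

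**Working it through.** **Plan's own figures.** The documents give no figure for this analysis. The design figure for patency is not in dispute and reproduces. With 125 lesions or subjects, at most 27 failures, a goal of 0.70 and an assumed rate of 0.82, the exact binomial gives a one-sided type I error of 0.0230 and power of 87.6%, against the stated 87%.

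**Definitions side by side.**

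| What happens to the lesion | Patency, SAP 7.6.1 | Curve, SAP 9.11.11 |
|---|---|---|
| Total occlusion, not re-treated | Failure | Censored at last contact alive |
| Total occlusion, re-treated | Failure | Event, at the re-treatment date |
| Clinically driven re-intervention or bypass of the stented segment | Failure | Event |
| Re-intervention not clinically driven, no occlusion | Not a failure | Event |
| Treatment of a non-target lesion in the target vessel | Not a failure | Event |
| None of these | Patent | Censored |

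Row 1 makes the curve look better than patency; rows 4 and 5 make it look worse. Row 4 rests on the SAP definition, which attaches the clinically driven condition to re-intervention. The wording in Protocol 2.2 is less clear on this.

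**Worth of one lesion.** Inputs: 68 subjects (SAP 6.1) and 1.2 lesions per subject (SAP 5.2, reported from another trial, so an assumption here).

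- 68 × 1.2 = 81.6, about 82 lesions.
- One misclassified lesion: 1/82 = 1.2 points. One row-1 lesion and one row-4 lesion roughly cancel.
- Protocol Table 6 anticipates total occlusion below 2%: 0.02 × 82 = 1.6 lesions. This is a ceiling with no time frame that covers treated and untreated occlusions, so the number lost to censoring could be zero.

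**Illustration of row 1 alone, on assumed data.** Kaplan-Meier, S(t) = ∏(1 − d/n) over event times up to day 273. Assumed: 7 re-interventions spread over days 60 to 260, 8 dropouts spread over days 30 to 265, the remaining lesions followed throughout, and 1 or 2 untreated occlusions.

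| Lesions | Free of target vessel revascularization | Patency, 1 occlusion | Patency, 2 occlusions |
|---|---|---|---|
| 82 | 91.0% | 89.7% (1.3 points lower) | 88.4% (2.6 lower) |
| 68 | 89.0% | 87.5% (1.5 lower) | 85.8% (3.2 lower) |

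The revascularization estimate does not move when occlusions are added, because each is censored. The illustration contains no row 4 or 5 events, so it is not an estimate of net bias.

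**Label and code.** PROC LIFETEST with no method option produces Kaplan-Meier estimates. That is the software's default, not something the SAP states. The code therefore agrees with SAP 8.1 and not with the words in 9.11.11. On the assumed data, actuarial estimates with monthly, 3-month or single 9-month intervals differ from Kaplan-Meier by less than 0.1 point. `STRATA TREAT` does nothing if TREAT has one level.

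**The case against.** The strongest reply is that SAP 6.2, the formal list of changes, promises only a revascularization analysis. Section 9.11.11 delivers that under the heading of safety and other parameters and never claims to estimate patency. On this view the fault is one loose sentence in 7.4. This stands in part: the authors may have meant the narrower analysis. But 7.4 names the primary efficacy endpoint, and the sections still have to be reconciled.

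Several stronger readings are tempting and are not supported:

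- *The patency result misses occlusions.* It does not. The binary analysis counts total occlusion as failure (7.6.1, 9.9.1).
- *Nothing else bears on patency.* The SAP also plans a per-protocol run, DUS results at 30 days and 9 months, core laboratory angiography, clinically driven and incidental revascularization rates, and secondary patency.
- *Patency will be overstated by a known amount.* The two mismatches pull in opposite directions, and no net size can be derived.
- *The code swaps events and censorings.* Only under a coding that no section states. What is shown is an undefined variable.
- *The revascularization curve omits 27 of 36 months.* Only the quoted probability is limited to 9 months. The code, the censoring rule and the cumulative incidence plot carry no such limit. The mortality curve is limited ("The Kaplan-Meier estimate of the death free-survival curve by 9-months of study follow-up will be presented"), but deaths are also counted throughout the study and listed with dates.

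The mock tables cited in SAP 11 were not available and may add detail.

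**Conclusion.** The concern holds as a mismatch between a promised analysis and the only one specified. SAP 7.4 promises time-to-event support for patency, 6.2 describes something narrower, and 9.11.11 defines a different event, with a censoring rule that treats an untreated total occlusion as event-free. The resulting curve should not be offered as support for the patency rate.

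The consequence is limited to that supportive analysis, because the primary result is unaffected and SAP 2 and 6.2 make all inference descriptive. The direction and size of any net error are not established. The 1.2 points per lesion depends on the borrowed ratio of 1.2 lesions per subject. The life-table label, `STRATA TREAT` and the undefined censor coding are tidying matters. The correction is worth making before the analysis is run, but it is not critical.

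**What to change.** 1. **Reconcile SAP 6.2, 7.4 and 9.11.11** by adding to 9.9 a lesion-level time to loss of primary patency. The event is the first of total occlusion (dated at the detecting DUS or angiogram), clinically driven re-intervention, or bypass, as counted in 7.6.1.
2. **Censor at the last patency assessment.** Contact alive does not show that the stent was open.
3. **Report the Kaplan-Meier estimate at day 303**, the end of the 9-month window in SAP 7.4, with an interval that allows for two lesions in one subject. DUS is scheduled only at 30 days and 9 months, so a reading at the target day, 273, would miss silent occlusions first found on days 274 to 303. Show numbers at risk across days 243 to 303, because the risk set thins as lesions are scanned. Count days as in 7.4, with the procedure as day 0; the 9.11.11 formula adds one day.
4. **Keep target vessel revascularization** as a separate safety curve.
5. **Tidy 9.11.11:** replace life-table with Kaplan-Meier to agree with 8.1 and the code, delete `STRATA TREAT`, and state the censor coding.

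Extending the mortality curve to 36 months is optional.

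The cost is SAP wording and minor programming. DUS dates are in the 9.11.8 listing, and 9.11.11 already needs revascularization dates. The angiogram date is not named in the 9.11.10 listing, so confirm that it is available by lesion.
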